## **1. Background**

Powerlifting-based resistance training is widely used to improve muscular strength, neuromuscular adaptations, and athletic performance. In recent years, interest has increased in understanding the physiological responses associated with structured strength training programs, particularly their effects on hormonal, metabolic, and lipid profile parameters. Hormonal responses such as testosterone, cortisol, growth hormone, and thyroid hormones play a critical role in adaptation to resistance exercise. Additionally, metabolic and lipid profile markers provide valuable information regarding cardiometabolic health and training-induced adaptations. However, evidence regarding short-term powerlifting-based interventions in trained athletes remains limited. This study aims to investigate the physiological effects of a structured powerlifting-based training program in male athletes using a randomized controlled design.

## **2. Objectives**

### **Primary Objective**

To evaluate the effects of a powerlifting-based training program on hormonal parameters in athletes.

### **Secondary Objectives**

To examine changes in metabolic markers following the intervention

To assess alterations in lipid profile parameters

To compare outcomes between intervention and control groups

## **3. Study Design**

This study is designed as a randomized controlled trial with a parallel-group design.

**Study Type:** Interventional

**Allocation:** Randomized

**Masking:** None (Open Label)

**Number of Arms:** 2

**Study Duration:** 8 weeks

**Study Setting:** University-based sports science laboratories

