### **6. Outcome Measures**

#### **Primary Outcomes**

Measured at baseline and after 8 weeks:

Serum total testosterone (ng/dL)

Serum cortisol (μg/dL)

Serum growth hormone (ng/mL)

Serum thyroid-stimulating hormone (μIU/mL)

Serum triiodothyronine (ng/dL)

Serum thyroxine (μg/dL)

(All measured using ELISA methods)

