#### **Secondary Outcomes**

Fasting insulin ( $\mu$ IU/mL)

Fasting blood glucose (mg/dL)

Total cholesterol (mg/dL)

LDL cholesterol (mg/dL)

HDL cholesterol (mg/dL)

Triglycerides (mg/dL)

(All analyzed using automated biochemical analyzers)

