## **7. Statistical Analysis**

Data will be analyzed using appropriate statistical software.

Descriptive statistics will be calculated for all variables.

Normality will be assessed using the Shapiro–Wilk test.

Between-group comparisons will be performed using independent samples t-tests or non-parametric equivalents.

Within-group comparisons will be performed using paired t-tests.

Statistical significance will be set at  $p < 0.05$ .

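### Masking is set to none for every role, although all twelve outcomes are laboratory results and the laboratory and data analyst could be masked cheaply

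*Protocol*

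**What the plan says.** Protocol Section 3 (Study Design) describes a randomised two-arm parallel trial and gives masking as "None (Open Label)". No role is singled out as masked.

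Section 6 lists six primary outcomes, all serum hormones, taken at baseline and week 8, with the note "All measured using ELISA methods". The six secondary outcomes are metabolic and lipid markers, with the note "All analyzed using automated biochemical analyzers".

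Section 7 (Statistical Analysis) lists a Shapiro–Wilk check and then states: "Between-group comparisons will be performed using independent samples t-tests or non-parametric equivalents". It adds: "Within-group comparisons will be performed using paired t-tests".

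The protocol does not mention coded samples, a masked laboratory, a masked analyst, or how samples are allocated to assay runs.

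**The concern.** Open label is unavoidable for those who do or supervise the lifting. It is not unavoidable for those who handle tubes and data. Section 3 makes no such distinction and so waives masking for two roles in which it is feasible.

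Every outcome passes through those two roles. ELISA values are read by an instrument, but people decide which samples to re-run, which replicates to reject and what to do with outlying values. At the analysis stage, someone decides between a t-test and a non-parametric test. If these people know the arm, their decisions can lean, even unintentionally, towards the expected hormonal response. The six hormones make up the whole primary objective, so these decisions arise six times there. Decisions made during assay are also hard to undo afterwards.

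**Working it through.** The protocol states no figure on this point, so there is nothing to reproduce. The check sets the sections side by side, then uses assumed inputs for scale.

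**1. Which roles could be masked?**

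| Role | Contact with the intervention | Can be masked? |
|---|---|---|
| Participants | Train or do not train (Section 5) | No |
| Trainers | Supervise the sessions (Section 5) | No |
| Laboratory staff | Need only serum tubes (Section 6) | Yes, with tubes coded to hide the arm |
| Data analyst | Needs only a dataset (Section 7) | Yes, with a coded arm variable |

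Section 3 has one entry covering all four rows.

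**2. How much passes through the two maskable roles?** Six primary outcomes plus six secondary outcomes make 6 + 6 = 12 of 12. None is rated by a participant or trainer.

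**3. What discretion does the text leave?** In the laboratory: re-runs, replicate rejection and outlying values, none of which the protocol addresses. In the analysis: Section 7 permits a t-test or an unnamed non-parametric equivalent. Shapiro–Wilk is listed, but no sentence ties its result to the choice of test.

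**4. Scale, under assumed inputs.** The protocol gives no sample size, standard deviation or assay precision. All rates below come from simulations with no true effect and a nominal 5% level.

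- *Choice of test.* 15 or 20 per arm, normal or lognormal data, 5,000 trials. A single t-test rejects in 4.3–5.3%. Keeping the better of t-test and Mann–Whitney rejects in 5.4–6.1%; a second run gave 5–6.5%. The simulation standard error is about √(0.05 × 0.95 / 5,000) = 0.003, or 0.3 percentage points. The excess over 5% is therefore at most about 1.5 points.
- *Selective re-assay.* Lowest 20% of one arm's results re-run, assay coefficient of variation 8–12%. The rate is 5.6–7.2%, an excess of 0.6 to 2.2 points.
- *Adding outlier removal.* If the analyst may also drop values beyond 2 SD and keep the best result, the rate is 10–14% across the two runs. Section 7 contains no such rule, so this shows what unrestrained discretion could do and does not describe the plan.

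**5. Is assay-plate layout part of the masking point?** Write an observed log value as the true log value plus a plate shift *s*.

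- Within-person change = true change + (*s* at week 8 − *s* at baseline). If the two visits are on different plates, the shift enters the paired test.
- Between-arm difference in mean change: if both arms share plates at each visit, the same term appears in both arms and cancels.
- If each person's two samples share a plate, *s* cancels within the person, even when the arms are on different plates.
- If only week-8 values are compared and the arms are on different plates, the shift does not cancel. Section 7 does not say whether changes or week-8 values are compared.

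Who is masked appears in none of these lines. A masked laboratory can still split visits across plates, and an unmasked one can balance them. Plate layout is a separate matter.

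**The case against.** The strongest reply is that the outcomes are instrument-read, so an unmasked laboratory has little influence. The Shapiro–Wilk check also narrows the choice of test, and a statistical analysis plan that is not shown may provide for a masked analysis. Most of this stands as to size: the inflation from re-assay or choice of test alone is a point or two. Moreover, a coded arm variable does not by itself stop an analyst from computing both p-values; the protection comes from settling the choice before the groups are compared. What the reply does not remove is that the protocol's own masking entry says none, for roles where masking costs little.

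Three stronger readings are tempting and are not supported.

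- A reader might infer that laboratory staff and the analyst do know the arm. Section 3 does not say so. Nothing indicates that tubes or datasets carry arm labels; the protocol only fails to prevent it.
- A reader might infer that open label lets plate-to-plate variation bias all six primary outcomes. The protocol is silent on plates, a detail commonly left to a laboratory manual, and masking would not fix the layout. The plausible pattern, with visits on separate plates and arms together, leaves the randomised comparison intact and affects only the within-group paired tests. False-positive rates for arms on separate plates depend on a layout that the protocol does not state, so they are not evidence against the masking choice.
- A reader might take 10–14% as the size of the problem. It requires an outlier rule that Section 7 does not contain.

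**Conclusion.** The point holds as a cheap improvement to a stated design choice. Section 3 applies an unavoidable open label to two roles where it is avoidable, and all twelve outcomes pass through those roles. The likely inflation is small to modest: up to about 2 percentage points above a nominal 5% in the simulated cases that correspond to re-assay or to the choice of test in Section 7. Those figures rest on assumed sample sizes, distributions and assay precision. The true size cannot be derived from the protocol, and actual bias has not been shown.

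**What to change.** In Section 3, replace the single masking entry with: participants and trainers unmasked; laboratory staff and data analyst masked. Label tubes with a study code that does not reveal the arm, and give the analyst a dataset with a coded arm variable. Settle re-runs, exclusions and the choice of test before the groups are compared, and break the code only at data lock.

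As an optional laboratory safeguard, separate from masking, assay each participant's baseline and week-8 hormone samples on the same plate, with both arms balanced across plates. This mainly protects the planned within-group paired tests. The person holding the code can draw up the plate list so that the laboratory stays masked.

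The cost of masking is coded labels and someone outside the laboratory and the analysis to hold the code. The plate safeguard adds about 8 weeks of frozen storage for baseline serum, and baseline hormone results become available only at the end. Neither needs more participants or visits.

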## **4. Participants**

### **Inclusion Criteria:**

Male athletes aged 18–24 years

Minimum of two years of regular sports participation

Actively training in basketball

Voluntary participation with written informed consent

### **Exclusion Criteria:**

Musculoskeletal injury or surgery within the last 6 months

Presence of chronic disease or metabolic disorder

Use of hormonal or performance-enhancing substances

Participation in another structured training program

### **5. Interventions**

#### **Arm 1: Powerlifting-Based Training Group**

Participants will perform a structured powerlifting-based training program in addition to their regular basketball training.

#### **Training characteristics:**

**Frequency:** 3 sessions per week

**Duration:** 8 weeks

**Session length:** ~60 minutes

**Exercises:** Squat, bench press, deadlift

**Intensity:** Progressive loading

**Additional components:** accessory exercises and core training

**Supervision:** All sessions supervised by qualified staff

#### **Arm 2: Control Group**

Participants will continue their usual basketball training routines without any additional strength or powerlifting-based exercises.

### **6. Outcome Measures**

#### **Primary Outcomes**

Measured at baseline and after 8 weeks:

Serum total testosterone (ng/dL)

Serum cortisol (μg/dL)

Serum growth hormone (ng/mL)

Serum thyroid-stimulating hormone (μIU/mL)

Serum triiodothyronine (ng/dL)

Serum thyroxine (μg/dL)

(All measured using ELISA methods)

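### Does the protocol need to fix the interval between the last training session and the hormone blood draw?

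*Protocol*

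**What the plan says.** The only timing given in Section 6 (Primary Outcomes) is "Measured at baseline and after 8 weeks". It covers testosterone, cortisol, growth hormone, TSH, T3 and T4, all by ELISA. Under Secondary Outcomes, insulin and glucose are named as fasting measures. No such label is attached to the hormones.

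Section 5 gives the training arm three supervised powerlifting sessions a week for 8 weeks, "in addition to their regular basketball training". The control arm keeps its usual basketball "without any additional strength or powerlifting-based exercises".

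Section 1 explains the choice of outcomes: "Hormonal responses such as testosterone, cortisol, growth hormone, and thyroid hormones play a critical role in adaptation to resistance exercise". Section 7 names the test: "Between-group comparisons will be performed using independent samples t-tests or non-parametric equivalents". No section states a rest period or clock time for sampling, or says that draw times are recorded.

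**The concern.** Serum hormones can reflect what a person did recently as well as how the body has adapted over weeks. Here one kind of recent activity, the powerlifting session, exists in one arm only and only after baseline. If blood at the post-test were taken while a response to the last session persisted, that response would be one-sided. Randomisation would not balance it, because it comes from the assigned treatment. Subtracting baseline would not remove it, because it was absent then. Neither the paired nor the independent-samples test in Section 7 could separate it from an adaptation built up over 8 weeks.

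All six primary outcomes would share the weakness. Nor is this obviously a matter for a statistical analysis plan: when blood is drawn is study conduct, and no analysis can recover an interval that was neither controlled nor recorded.

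**Working it through.** **1. What the document fixes and leaves open.**

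| Item | Where | Content |
|---|---|---|
| Hormone draws | Section 6, Primary Outcomes | Baseline and after 8 weeks; nothing on time of day or rest |
| Fasting | Section 6, Secondary Outcomes | Insulin and glucose only |
| Powerlifting | Section 5, Arm 1 | 3 sessions a week for 8 weeks |
| Basketball | Section 5, both arms | Continues in both |
| Test | Section 7 | Independent-samples t-test or non-parametric equivalent, p < 0.05 |
| Duration of any response to a session | – | Not given |
| Sample size, SDs | – | Not given in the text at hand |

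The one-sided part can come only from powerlifting. Basketball continues in both arms and is not one-sided by design.

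**2. What must be true for harm.** Three things are needed together: (a) a session changes the hormone; (b) the change lasts until the draw; (c) what remains is large relative to the between-person SD. Section 1 gives some support to (a). Nothing in the document bears on (b) or (c).

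The fasting requirement bears on (b). If one sample serves all twelve analytes, as is natural when the visits coincide, a draw immediately after a session is unlikely. What remains open is a session on the preceding day.

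**3. How large a leftover would matter (illustration only).** The plan has no figure to reproduce. The assumptions are: no lasting effect, equal arms of n, outcome SD 1, a shift of d SD in the training arm at the post-test, and a two-sided 5% t-test (the protocol does not state sidedness). The t statistic then follows a noncentral t distribution with 2n − 2 degrees of freedom and noncentrality d × √(n/2).

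- n = 15: √7.5 = 2.739, so d = 0.25 gives 0.25 × 2.739 = 0.685 and d = 0.5 gives 1.369.
- n = 30: √15 = 3.873, so d = 0.25 gives 0.968 and d = 0.5 gives 1.936.

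Chance of p < 0.05 for one hormone:

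| d (SD) | n = 15 | n = 20 | n = 30 |
|---|---|---|---|
| 0 | 0.050 | 0.050 | 0.050 |
| 0.05 | 0.052 | 0.053 | 0.054 |
| 0.10 | 0.058 | 0.061 | 0.067 |
| 0.25 | 0.101 | 0.120 | 0.159 |
| 0.50 | 0.262 | 0.338 | 0.478 |

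A normal approximation gives 0.105 and 0.278 at n = 15, and 0.162 and 0.491 at n = 30, for d = 0.25 and 0.5. The largest gap from the t values is 0.278 − 0.262 = 0.016.

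If only some of the training arm is drawn while a response persists, the mean shift shrinks in proportion. With half the arm at 0.5 SD the mean shift is 0.5 × 0.5 = 0.25 SD, and simulation gives 0.100 (n = 15) and 0.156 (n = 30). With a quarter it is 0.25 × 0.5 = 0.125 SD, giving 0.064 and 0.075.

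**4. Reading the table.** It is the power curve of a t-test, with the shift called an error instead of an effect. It shows that a mean shift below about 0.1 SD hardly matters and that one of about 0.25 SD or more would. It cannot say which applies here, because both n and d are assumed.

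**The case for a change.** The strongest case for acting is that the remedy is cheap and the exposure covers every primary outcome. A sentence stating shared sampling conditions, and a log of draw times, would cost little when a fasting visit is already planned. Fasting alone does not settle whether the last session was the day before or several days earlier. Supervision of all sessions may make session dates recoverable, but the protocol does not say that these or the draw times are kept. All of this is fair, and the omission stands as a fact.

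It does not establish a defect. The step from unstated timing to a biased result needs a time course for these hormones that the document does not contain. Any conviction that one exists would come from outside it.

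The label of false positive also assumes more than the protocol claims. The primary objective in Section 2 is the effect of the programme on hormones, and it is not limited to lasting adaptation. A response to the programme's own sessions is caused by the randomised programme, so the between-group difference remains a valid comparison of the two assignments. What is uncertain is how much of it to call adaptation, which is a question of interpretation. That uncertainty is worth a line in the trial report, but it does not make the comparison wrong.

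**Conclusion.** No change to the plan is called for. The protocol is silent on the conditions of the hormone draw, but it states no rule that would give a wrong answer, and nothing in it contradicts the sensible practice of taking all analytes from one fasting sample under the same conditions in both arms. A laboratory following this plan would probably do that and note the draw times as routine.

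The size of any effect cannot be derived from the document. Under the assumptions above, the error rate for one hormone runs from about 5% (shift of 0.05 SD) to 26% at 15 per arm or 48% at 30 per arm (shift of 0.5 SD). Those figures show only when timing would matter and should not be cited as evidence about this trial.

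The conclusion rests on two readings: that the hormones share the fasting draw with insulin and glucose, and that both arms are sampled in the same way. It would change if study records showed training-arm blood taken at or straight after a session, or arms sampled under different conditions.

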#### **Secondary Outcomes**

Fasting insulin ( $\mu$ IU/mL)

Fasting blood glucose (mg/dL)

Total cholesterol (mg/dL)

LDL cholesterol (mg/dL)

HDL cholesterol (mg/dL)

Triglycerides (mg/dL)

(All analyzed using automated biochemical analyzers)

## **7. Statistical Analysis**

Data will be analyzed using appropriate statistical software.

Descriptive statistics will be calculated for all variables.

Normality will be assessed using the Shapiro–Wilk test.

Between-group comparisons will be performed using independent samples t-tests or non-parametric equivalents.

Within-group comparisons will be performed using paired t-tests.

Statistical significance will be set at  $p < 0.05$ .

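### Section 7's only between-group test either ignores the baseline hormone values or fixes their slope at 1; ANCOVA on a suitable scale is usually more precise at little cost

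*Protocol*

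**What the plan says.** The design is randomized: "This study is designed as a randomized controlled trial with a parallel-group design" (Section 3). The primary objective is "To evaluate the effects of a powerlifting-based training program on hormonal parameters in athletes" (Section 2), and a secondary objective is "To compare outcomes between intervention and control groups". Section 6 lists six primary hormones, all "Measured at baseline and after 8 weeks".

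Section 7 gives one method for comparing the arms: "Between-group comparisons will be performed using independent samples t-tests or non-parametric equivalents". It does not say whether the test is applied to 8-week values or to changes. It also states "Within-group comparisons will be performed using paired t-tests" and "Normality will be assessed using the Shapiro–Wilk test". ANCOVA, baseline adjustment and a group-by-time model appear nowhere in the protocol.

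For the metabolic and lipid markers Section 6 states no measurement times. A baseline is only implied, by the paired tests and, for the metabolic markers, by the objective "To examine changes in metabolic markers following the intervention".

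**The concern.** The between-arm difference in each hormone is what answers the primary objective in a randomized trial. The one method that certainly uses the baseline is the paired t-test, and it does not compare the arms. The between-arm test has two readings:

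- On 8-week values, the baseline gets a slope of 0 and is ignored.
- On changes, the baseline gets a slope of 1, whatever the data show.

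ANCOVA estimates the slope. If r is moderate, either reading gives a wider interval and less power than the same participants could provide. Nobody can know r for six different hormones in advance, so choosing between the two readings is a gamble that ANCOVA avoids.

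This is a point about efficiency. Neither t-test is biased or invalid.

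**Working it through.** **Inputs.** From the protocol: two randomized parallel arms (Section 3), baseline and 8-week values for each hormone (Section 6), and a 0.05 significance level (Section 7), taken as two-sided. The available text gives no sample size, SD, effect or r, so there is no planned figure to reproduce. Assumptions: n per arm 10 to 30 with equal arms, r from 0 to 0.7 in the simulations, equal SDs at both visits, and a difference of 0.8 SD.

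**Large-sample variance of the arm difference**, with the t-test on 8-week values set to 1:

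- 8-week t-test: 1
- change t-test: 2(1 − r)
- ANCOVA: 1 − r²

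ANCOVA relative to the 8-week test is therefore 1 − r². Relative to the change test it is (1 − r²) / [2(1 − r)] = (1 + r)/2. Neither ratio exceeds 1.

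**Small-sample penalty.** Estimating one slope multiplies the ANCOVA variance by f = 1 + 1/(2n − 4). This is 1.0625 / 1.0385 / 1.0278 / 1.0179 at n = 10 / 15 / 20 / 30 per arm.

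**Results at 15 per arm:**

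| | r = 0.3 | r = 0.5 | r = 0.7 |
|---|---|---|---|
| 1 − r² | 0.91 | 0.75 | 0.51 |
| (1 + r)/2 | 0.65 | 0.75 | 0.85 |
| (1 − r²) × 1.0385 | 0.945 | 0.779 | 0.530 |
| (1 + r)/2 × 1.0385 | 0.675 | 0.779 | 0.883 |
| Ratio to the better t-test | 0.945 (8-week) | 0.779 (tie) | 0.883 (change) |
| n per arm that t-test needs to match (15 / ratio) | 15.9 | 19.3 | 17.0 |

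The comparisons with the 8-week test and with the change test are alternatives. They do not add.

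**Simulated power** (normal data, 0.8 SD effect, 40,000 runs per cell):

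| n per arm, r | 8-week t | change t | ANCOVA |
|---|---|---|---|
| 15, 0 | 55.7% | 31.8% | 54.2% |
| 15, 0.3 | 56.0% | 43.2% | 58.5% |
| 15, 0.5 | 56.0% | 56.1% | 66.7% |
| 15, 0.7 | 56.4% | 78.1% | 83.0% |
| 10, 0 | 39.5% | 22.3% | 37.4% |
| 30, 0.5 | 86.3% | 86.1% | 93.7% |

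At 15 per arm and r = 0.3 / 0.5 / 0.7, the mean 95% interval from ANCOVA is 0.97 / 0.88 / 0.73 times as wide as from the 8-week test, and 0.82 / 0.88 / 0.94 times as wide as from the change test. Type I error per test was 0.048 to 0.053 for all three methods in every cell. This says nothing about the family of six primary outcomes: with six independent true nulls, any of these methods gives 1 − 0.95⁶ = 26% chance of at least one p < 0.05.

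**Where the gain ends.**

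- Against 8-week values, (1 − r²)f = 1 at r = 0.24 / 0.19 / 0.16 / 0.13 for n = 10 / 15 / 20 / 30. Below that there is no gain.
- Against change, (1 + r)f/2 = 1 at r = 0.88 / 0.93 / 0.95 / 0.97. Above that there is no gain.

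**Skewed data** (lognormal, log SD 1, effect 0.8 log-SD, 15 per arm, r on the log scale, 20,000 runs):

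| | r = 0.3 | r = 0.5 | r = 0.7 |
|---|---|---|---|
| ANCOVA, log scale | 58.5% | 67.0% | 82.8% |
| ANCOVA, untransformed | 39.6% | 44.4% | 57.3% |
| Mann-Whitney, 8-week values | 52.2% | 52.3% | 52.7% |
| Mann-Whitney, change | 42.7% | 53.4% | 73.2% |

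With log SD 0.5, untransformed ANCOVA has 53.2 / 60.1 / 75.9%.

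**The case against.** The strongest reply is that nothing here is wrong. The named tests are valid, Section 7 is only an outline, and baseline covariates and transformations are ordinary SAP content; a SAP that was not available for this review may deal with them. That rules out calling this an error. It does not remove the point, because Section 7 is not silent: it names a specific test for the primary outcomes, and a SAP using ANCOVA would depart from it.

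The size is also assumed throughout. Against the better t-test at 15 per arm, the gain is about 2.5, 11 and 5 points at r = 0.3, 0.5 and 0.7. The middle value is the most favourable, because the two t-tests tie there. This stands, and the true gain is unknown. But the better t-test cannot be picked in advance. Against the worse one, the gain is about 15 points at r = 0.3 (58.5 − 43.2) and 27 at r = 0.7 (83.0 − 56.4).

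Finally, the low cost depends on the scale. With strong skew, untransformed ANCOVA loses up to 16 points (57.3 against 73.2%) to a rank test that Section 7 already allows. This stands too, and it is why the scale must be fixed along with the model.

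**Conclusion.** The point holds as a recommended efficiency improvement to the primary analysis, with medium confidence. On either reading, the named test uses the collected baseline values less well than ANCOVA does over most of the plausible range of r. At an assumed 15 per arm, ANCOVA's variance is 0.95 / 0.78 / 0.88 of the better t-test's at r = 0.3 / 0.5 / 0.7. The result rests on equal SDs at the two visits, roughly normal data on the chosen scale, and the assumed n, r and effect. The gain can be nil, or slightly negative at the extremes of r. For metabolic and lipid markers the point applies only where a baseline is taken.

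**What to change.** Replace the between-group sentence in Section 7 with text such as:

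> The primary between-group analysis of each hormone is an ANCOVA of the 8-week value on arm and the baseline value of that hormone, reported as the adjusted mean difference with 95% CI. The scale (original or log) is fixed for each hormone from pooled baseline values, before outcomes are compared by arm. Hormones on the log scale use log baseline and log 8-week values and are reported as an adjusted ratio of geometric means with 95% CI. Unadjusted two-sample t-tests or their rank-based counterparts are sensitivity analyses. The same model is used for metabolic and lipid markers where a baseline is taken.

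Two drafting details should be settled at the same time: the criterion that selects the scale (and whether the Shapiro–Wilk test, applied to pooled baseline values, serves as it), and a pre-stated fallback for a hormone that suits neither scale.

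The cost is a few sentences, no new hormone data, and one degree of freedom per outcome. If r is near zero, power falls by about 2 points at 10 per arm (39.5 to 37.4%) and 1.5 at 15 (55.7 to 54.2%).

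### The randomized between-group comparison is only a secondary objective, and within-arm paired tests have equal standing, so a training-arm change alone could be taken as meeting the primary objective

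*Protocol*

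**What the plan says.** Section 3 of the protocol fixes the design: "This study is designed as a randomized controlled trial with a parallel-group design". Under Arm 2, Section 5 defines the comparator: "Participants will continue their usual basketball training routines without any additional strength or powerlifting-based exercises". The training arm adds the powerlifting program to its regular basketball training.

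The primary objective in Section 2 is "To evaluate the effects of a powerlifting-based training program on hormonal parameters in athletes". It names no comparator. The contrast between the arms appears separately, as the last of three secondary objectives: "To compare outcomes between intervention and control groups".

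Section 6 lists six serum hormones as primary outcomes, measured at baseline and at 8 weeks.

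Section 7 then gives two kinds of test: "Between-group comparisons will be performed using independent samples t-tests or non-parametric equivalents" and "Within-group comparisons will be performed using paired t-tests". It does not say which of them answers the primary objective. One threshold covers both: "Statistical significance will be set at" p < 0.05.

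**The concern.** In a randomized trial, the contrast between arms is what identifies the effect of the intervention. Here the objectives rank that contrast below the primary objective, and the analysis section supplies another test, the paired t-test within an arm, at the same significance level. A report could therefore state that testosterone or cortisol changed significantly in the training arm, call the primary objective met, and still be consistent with the protocol's wording.

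That conclusion would be unsafe. Both arms keep training in basketball for 8 weeks, so hormone levels may move in both for reasons unrelated to powerlifting, such as the stage of the season, training load or assay drift. A paired test in one arm counts all such movement as if it were the program's effect. The control arm was randomized to remove exactly this.

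**Working it through.** The protocol text at hand gives no sample size, power or effect size, so there is no planned figure to reproduce. The check sets the sections side by side and then sizes the consequence under stated assumptions.

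**Step 1: the sections together.**
- Design (Section 3): randomized, two parallel arms.
- Primary objective (Section 2): effects on hormones, comparator not named.
- Between-group comparison (Section 2): secondary.
- Tests (Section 7): between-group and paired, one threshold, neither named as primary.

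Listing the comparison separately as secondary leaves open that the primary objective is answered some other way. The paired test is the only other inferential test in Section 7.

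**Step 2: how often a paired test misleads when training does nothing.**

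Inputs:
- Threshold 0.05 (Section 7), taken as two-sided because sidedness is not stated.
- n per arm: assumed 10, 15, 20 and 30.
- d: an assumed drift common to both arms, in SDs of the change score. The main case is 0.3, with 0.2 and 0.5 as a range.
- Training effect: zero.

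The paired statistic follows a noncentral t distribution with n − 1 degrees of freedom and noncentrality d√n. The chance of significance is P(|T| > t₀.₉₇₅,ₙ₋₁).

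Noncentrality at d = 0.3:
- n = 10: 0.3 × √10 = 0.949
- n = 15: 0.3 × √15 = 1.162
- n = 20: 0.3 × √20 = 1.342
- n = 30: 0.3 × √30 = 1.643

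Chance that one training-arm paired test is significant:

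| n per arm | d = 0.2 | d = 0.3 | d = 0.5 |
|---|---|---|---|
| 10 | 0.088 | 0.136 | 0.293 |
| 15 | 0.112 | 0.192 | 0.438 |
| 20 | 0.136 | 0.247 | 0.565 |
| 30 | 0.185 | 0.355 | 0.754 |

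In the between-group test the common drift cancels, so its false-positive rate stays at 0.05 in every cell. The paired test gets worse as the sample grows, because it detects the drift correctly and the error lies in attributing it to training. With no drift (d = 0), a single paired test also has a rate of 0.05.

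**Step 3: conditional context on the six hormones.** The protocol gives no rule for reading six primary outcomes together. If any one significant between-group result were read as an overall hormonal effect, and there were none, the false-positive chance with independent hormones would be 1 − 0.95⁶ = 1 − 0.735 = 0.265. Simulation with equally correlated hormones gives about 0.21 at an assumed correlation of 0.5 and about 0.11 at 0.9. Holm adjustment over the six tests brings this to about 0.05 with independent hormones and about 0.02 at correlation 0.9. If each hormone is reported as a separate question, each test has a rate of 0.05 and there is no inflation to correct.

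**The case against.** The best defence is that the protocol already implies the right comparison. Its Background says that the study uses a randomized controlled design, Section 3 repeats this, and Section 5 defines a usual-training control. An effect of a program in such a trial is naturally an effect relative to control. The third secondary objective speaks of outcomes in general, follows the metabolic and lipid items, and may be a loosely placed catch-all. Section 7 lists the between-group test first. Nothing says that a training-arm change is sufficient.

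Much of this stands. The protocol does not state that a within-arm change meets the primary objective, and a reader who infers that the sponsor intends to claim success that way goes beyond the text. But the implied reading does not undo an explicit ranking. Section 2 names the group comparison and places it among the secondary objectives, and Section 7 does not make the paired tests subordinate.

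A second objection concerns the six hormones. Multiplicity rules are commonly left to the SAP, which is not shown. Holm-adjusted p-values compared with 0.05 would not conflict with Section 7. This stands in full. A reader might infer that the trial runs a 26.5% false-positive risk by design. The protocol does not support that: it states no any-one rule, claims no familywise error rate, and naming several primary outcomes is not in itself an error.

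**Conclusion.** The point holds for the rank of the between-group comparison and the role of the paired tests. Both are fixed in the protocol's own Sections 2 and 7, so the correction belongs there and not only in an SAP.

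Its size depends on drift. For an assumed 0.3 SD drift common to both arms and no training effect, a single training-arm paired test is significant with probability about 0.14 to 0.36 for 10 to 30 per arm, against 0.05 between groups. The drift and the sample sizes are assumptions. With no drift, a single paired test carries no excess error, but the protocol gives no ground for assuming that.

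The multiplicity figures (26.5% with independent hormones, about 11% at correlation 0.9) apply only if one significant hormone were read as an overall effect. They are context for a sentence worth adding, not evidence of an error in the plan. A reader might also want one combined error rate for between-group and paired tests. None is offered, because it would need assumptions about drift, the success rule and correlation that the document does not settle.

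This should be fixed before analysis. Confidence is medium, because the sponsor may already intend the between-group reading.

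**What to change.** - **Section 2:** make the between-group comparison of the six hormones part of the primary objective. Keep it as a secondary objective only for the metabolic and lipid outcomes.
- **Section 7:** state that the between-group comparison is the primary analysis, and that the within-arm paired tests are descriptive and support no claim of a training effect.
- **Here or in the SAP:** if an overall claim of a hormonal effect is to be made, rest it on Holm-adjusted p-values over the six between-group tests. Otherwise say that the hormones are separate questions and that no overall claim will be drawn from any single one.

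The first two changes cost a few sentences and need no new data. What is given up is within-arm significance as evidence. The Holm option has a price in power: a test with 80% power at 0.05 has about 53% to 55% at Holm's first step (0.05/6 = 0.0083) for an assumed 15 to 30 per arm. Separate reporting avoids that loss but gives up the overall claim.
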